**Describe the following aspects of the study design:**

A.) Proposed study groups with number/group and treatments/group

Group 1: patients who undergo open surgical incision and drainage with debridement and irrigation (>20 patients)

Group 2: patients who undergo arthroscopic incision and drainage with debridement and irrigation (>20 patients)

B.) Describe the method used to determine the number of subjects needed

Power analysis utilized to determine a difference in the number of surgeries required to display apparent clinical resolution between open versus arthroscopic treatments (beta =0.80, alpha = 0.05) shows the optimal sample size to be a minimum of 40 patients.

C.) Describe how you determined that this number of subjects could be recruited

Power analysis. Additionally, [name] (CHRC/Research Manager MC EP Compliance) was contacted and was able to find a preliminary potential of 1,851 unique patient records from the year 2000 to the present who had septic arthritis. Even if only 20% of these patients met study inclusion/exclusion criteria, approximately 20 patients a year would be included. This would require 2-3 years of data collection in order to meet appropriate power analysis.

Anecdotally, the attending physicians serving as principal- and co-investigators believe they treat a minimum of 20 adult patients each per year with septic arthritis of the native knee.

D.) Method of randomization

Patients with medical record numbers ending in an EVEN number will undergo open surgical irrigation and debridement.

Patients with medical record numbers ending in an ODD number will undergo arthroscopic surgical irrigation and debridement.

E.) Schedule of events (i.e. control vs. treatment, number of visits)

All patients who present to the emergency department with a painful knee and clinical suspicion for septic arthritis undergo appropriate workup by the emergency department staff members. If there is a clinical suspicion for septic arthritis, the standard workup includes the following:

- assessment of vitals
- obtaining a history of the present illness
- performing an appropriate physical examination

If a provider determines that septic arthritis is part of their differential diagnosis, a basic serum laboratory workup is to be ordered. There will be a template created on the Cerner application to assist providers with a convenient, expedited manner of ordering these labs. These will include the following blood serum values:

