Vitals, physical exam findings, and laboratory markers will be recorded in the clinical record and maintained within the patient's electronic medical record. The principal investigator will utilize the electronic medical record to record and maintain pertinent physical examination findings, laboratory markers, and treatments on a private, secured device. The only individuals who will be granted access to the device are co-investigators participating in this research study.

F.) List of Key Variables or Measurements to be done

- initial presenting arthrocentesis labs as well as serum lab values
- physical examination findings
- time from presentation to operative management
- type of surgical approach performed
- total operative time
- reason for necessity to return to operating room
- number of operative procedures required in order to establish clinical improvement**
- bacterial growth from arthrocentesis and operative cultures
- length of antibiotic course as deemed by infectious disease specialist
- hospital length of stay**
- Lysholm knee scores

G.) Assessment of subject safety and development of a data and safety monitoring plan

All data will be stored on a password locked external hard drive device. The password will only be provided to primary investigators of this study. The information recorded will be maintained on this device and stored in accordance with TTUHSC policies. The principal investigator will be responsible for version control and will ensure the study data are shared among team members in a secure fashion in accordance with TTUHSC/UMC guidelines (e.g., encrypted email, restricted-access share portal). The original email communications will be permanently deleted from the principle investigator's email inbox, outbox, and deleted folders.

Any unanticipated problems or other adverse events will be reported to the TTUHSC Human Protections Administrator. All unanticipated problems involving risk to subjects or others, adverse events, and all concerns related or possibly related to the study will be reported promptly to the TTUHSC Human Research Protections Office by providing

initial notification of the event as quickly as possible after the research team's knowledge of the event, but within five (5) business days.

H.) Create and attach your data collection form

This has been completed and filed with the IRB submission.

I.) Methods of data analysis (statistical analysis)

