Both [name] and [name] have served as statisticians in their previous roles as research assistants and have advanced training in statistical analysis. Regardless, the finalized data will be submitted to Texas Tech statisticians for validation and confirmation. Some of the anticipated statistical analysis tests are as follows:

Independent samples t-tests will be used to compare means of continuous and ordinal variables and p values less than 0.05 will be considered to represent a significant difference. For variables with Levene's Test for Equality of Variances greater than 0.05, equal variance is assumed. Pearson Chi-Square test p-values less than 0.05 will be considered to represent a significant difference in categorical variables. Fischer's exact test less will not be utilized as NCDB groups with  $n < 10$  are not to be included. ANOVA will be used to calculate significant differences in continuous and ordinal variables that have more than two categories. Paired samples t test and repeated measures ANOVA will be used to determine the progression of individual patients over time for continuous and ordinal variables respectively. Wilk's Lambda p-value less than 0.05 will be considered significant for repeated measures ANOVA and pairwise comparison will be used to determine the location of significance. Binary logistic regressions will be used to calculate odds ratios. Multivariate binary logistic regression may be attempted for all

significant variables. Receiver Operator Characteristic (ROC) may be calculated for significant continuous variables to determine the existence of a threshold that maximized sensitivity and specificity. All analysis will likely be performed by [name] on SPSS version 25 (IBM Corp. Released 2018. IBM SPSS Statistics for Macintosh, Version 25.0. Armonk, NY: IBM Corp).

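### The optional multivariable logistic model is filled by significance screening, so it need not contain the treatment arm, may adjust for consequences of surgery, and is unstable at 40 patients

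*Combined protocol and SAP*

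**What the plan says.** The statistical methods section (item I of the study design) introduces its content with "Some of the anticipated statistical analysis tests are as follows". It then states that "Binary logistic regressions will be used to calculate odds ratios", and that "Multivariate binary logistic regression may be attempted for all" significant variables. The threshold given in the same section is that "p values less than 0.05 will be considered to represent a significant difference".

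The section does not name the binary outcome of these regressions. It does not say that the arm is a required term, that predictors must be known before surgery, how many terms are allowed, or what to do when events are few. It also sets Fisher's exact test aside. It does not say whether significant means associated with an outcome or different between the arms.

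The list of key variables (item F) puts the surgical approach performed beside total operative time, reason for return to the operating room, hospital length of stay, Lysholm score and "length of antibiotic course as deemed by infectious disease specialist". The two starred outcomes are the number of operative procedures and length of stay, neither of which is binary.

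Separately from any regression, "Independent samples t-tests will be used to compare means of continuous and ordinal variables", and Pearson chi-square tests are planned for categorical variables.

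**The concern.** This is the only adjusted between-arm analysis that the plan mentions. A rule that admits terms because they are significant raises three problems.

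- The arm, the one variable that the trial is about, gets no protected place. An adjusted odds ratio for arm that appears only when arm was already significant is biased away from no effect.
- Several recorded variables arise at or after surgery. Length of stay is itself a main outcome, and a reason for return exists only in patients who had the event. Adjusting for such variables may not estimate the effect of the surgical approach.
- Forty patients yield few re-operations, and ordinary maximum-likelihood logistic regression behaves poorly with several terms and few events.

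At stake is the validity of any adjusted odds ratio that the trial reports, for the arm or for other predictors.

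**Working it through.** **The plan's own figure.** Item B describes a "Power analysis utilized to determine a difference in the number of surgeries required to display apparent clinical resolution" and reports ("beta =0.80, alpha = 0.05) shows the optimal sample size to be a minimum of 40 patients"). No effect size, SD or event rate is given, so 40 cannot be reproduced. Working back with 20 per arm, 80% power and two-sided 0.05:

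- Means: d = (1.960 + 0.842) × √(2/20) = 0.886 (0.909 from the t distribution).
- Proportions: 50% v 10% gives n = [1.960√(2 × 0.3 × 0.7) + 0.842√(0.25 + 0.09)]² / 0.4² = 19.4, so 20 per arm and 40 in total.

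These only show what size of effect fits N = 40. **All re-operation rates below are assumptions.**

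**1. Does the arm survive the screen?** Take the outcome as any repeat operation, with i and j events in arms of n = 20. The Pearson screen keeps the arm if X² = 2n[i(n−j) − j(n−i)]² / [n²(i+j)(2n−i−j)] exceeds 3.84. For example, 8 v 2 events gives 40 × 120² / (400 × 10 × 30) = 4.80 and the arm stays. With 7 v 2, X² = 40 × 100² / (400 × 9 × 31) = 3.58 and it goes. A Wald screen needs |log OR / SE| > 1.96, with SE = √(1/i + 1/(n−i) + 1/j + 1/(n−j)). Summing binomial probabilities over all tables:

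| Assumed rates | Expected events | Chi-square drops arm | Wald drops arm |
|---|---|---|---|
| Equal, 10–40% | 4–16 | 95–96% | more often |
| 30% v 15% | 9 | 80% | 86% |
| 40% v 15% | 11 | 56% | 64% |
| 40% v 10% | 10 | 38% | 54% |
| 50% v 10% | 12 | 16% | 31% |
| 40% v 5% | 9 | 18% | 58% |

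The Wald figures are worse partly because a table with no events in one arm has no finite estimate and never passes. The chance of no events in an arm of 20 is 0.90²⁰ = 12% at 10% risk and 0.95²⁰ = 36% at 5% risk. If counts of operations with about 78% t-test power are reduced to yes/no, the chi-square screen drops the arm in 24–35% of trials.

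**2. How many terms can the data carry?** At 20–40% overall re-operation, events = 40 × 0.20 to 40 × 0.40 = 8 to 16. Events per term are 1.6–3.2 with 5 terms and 1.0–2.0 with 8. In simulated 40-patient models of fixed size that always included the arm (400 runs per setting, assumed covariate effects), separation or a failed fit occurred in 0–11% of runs with 1–5 terms and 4–19% with 8. With 8 terms the median arm log odds ratio was:

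- −2.01 against a true −1.35 (30% v 10%): ratio 1.49
- −1.39 against −0.98 (40% v 20%): ratio 1.42
- −3.14 against −2.20 (50% v 10%): ratio 1.43

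So it was about 40–50% too large. With no true effect (30% in both arms) it stayed centred near zero. Screening adds its own inflation: with 12 pure-noise candidates and 30% events, at least one enters in roughly 36–40% of trials, with a median odds ratio of 2.7 per SD.

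**3. What does post-operative adjustment do?** It depends on the variable's causal role. In large simulated samples, a post-operative variable that carries the whole effect moved the arm odds ratio from 0.38 (or 0.62 for a weaker effect) to about 1.0. A length of stay that was only a consequence of re-operation left it almost unchanged (0.265 to between 0.265 and 0.272). At N = 40 and 40% v 15%, assume that re-operation lengthens antibiotics by 1 SD and arthroscopy lengthens operative time by 1 SD. Adjusting for both then raised the SD of the arm log odds ratio from 0.83 to 1.37 and cut power from 40% to 25%.

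**The case against.** The strongest reply is that little depends on this model. It is optional, it sits in a list of anticipated tests, and the finalised data go to institutional statisticians for validation. The hypothesis and sample size concern the number of surgeries and length of stay, which are compared directly between arms. This stands. A reader might infer that the trial question cannot be answered, but the documents do not make the regression the primary analysis.

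A reader might also infer that the arm is usually dropped. That depends on the effect and on the screen. With chi-square, the test the plan names for categorical variables, the arm is kept in 62% of trials at 40% v 10% and 84% at 50% v 10%. The wording is also ambiguous. If significant means different between the arms, the screen does not test the arm at all, although it could then favour variables that surgery itself has changed.

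Nor do the figures show that the model routinely breaks down. Fits without a finite estimate are a minority, and the commoner harm is inflation and instability. The 36% chance of an empty arm needs a 5% risk that appears nowhere in the documents.

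Finally, item F is a list of measurements, not a declared list of model candidates. Post-operative variables are permitted, not certain to enter, and some would do little harm. What survives is that nothing in the rule prevents these problems.

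**Conclusion.** The concern holds for a supportive analysis. As written, the rule permits a model without the treatment arm, permits adjustment for consequences of surgery, and sets no limit on terms for a data set likely to hold few events. An arm odds ratio from such a model would be selected on its own significance, possibly over-adjusted, and about 40–50% too large on the log scale with 8 terms under the non-null settings examined.

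The frequency of losing the arm ranges from about 16% (50% v 10%) to about 95% (no effect) with a chi-square screen, and is higher with a Wald screen. This assumes that significant means associated with any repeat operation, 20 patients per arm, a two-sided 0.05 threshold, and re-operation rates that the documents do not supply. The main t-test and chi-square comparisons are untouched by this point.

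**What to change.** Replace the significance-screening sentence with one pre-specified supportive model:

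- **Outcome:** any repeat operation during study follow-up (yes/no), stated as supportive to the count of operations.
- **Terms:** assigned arm, always kept whatever its p-value, plus at most one or two presenting covariates named before the data are examined. CRP is one example because the presenting work-up already collects it. The documents do not single it out, and the choice is the investigators'.
- **Exclusions:** no variable measured at or after surgery, including operative time, antibiotic length, reason for return, length of stay and Lysholm score.
- **Estimation:** Firth penalised or exact logistic regression, with a confidence interval for the arm odds ratio.
- **Other predictors:** reported univariately and labelled exploratory.

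This changes analysis wording only and needs no new patients or data. It may need a software routine beyond SPSS 25. Fewer predictors are examined jointly, and a yes/no outcome discards information: for counts with about 78% t-test power, the chi-square test on any re-operation has about 65–76%. That is why the model should support the comparison of counts and not replace it.

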All non-english speaking persons will be offered study inclusion. Informed consent will be obtained utilizing a Spanish-translated consent form (after IRB approval). There are multiple Spanish speaking members of the research personnel and they will be obtaining Spanish consents. If one is not available, then a certified hospital interpreter will be utilized. If none are available, since UMC does not allow language line solutions to be used for research purposes, the patient will not be able to be consented and thus will not be included in the study.

C.) Indicate the population of subjects potentially able to participate in this study

All adult patients (>18 years) who have a clinically established diagnosis of septic arthritis in the emergency department based on the following will be considered for study inclusion and approached for offering participation in our study:

- Arthrocentesis with synovial WBC > 50,000 with left shift (85% PMNs)
- AcrySTALLINE (without gout crystals) elevated synovial WBC >25,000 with high clinical suspicion
- Willingness to participate in this research study

These patients are all indicated with formal operative irrigation and debridement of their knee, regardless of study inclusion. However, they will be excluded from study inclusion if they meet one of the following exclusion criteria:

- Recently treated septic arthritis (within past 3 months)
- If they have a prosthetic joint replacement to the affected knee
- Refusal to participate in the study

D.) Indicate the number needed

Our power analysis (beta =0.80, alpha = 0.05) shows the optimal sample size to be a minimum of 40 patients.

E.) List the inclusion/exclusion criteria

All adult patients (>18 years) who have a clinically established diagnosis of septic arthritis in the emergency department based on the following will be considered for study inclusion and approached for offering participation in our study:

- Arthrocentesis with synovial WBC > 50,000 with left shift (85% PMNs)
- AcrySTALLINE (without gout crystals) elevated synovial WBC >25,000 with

high clinical suspicion  
-Willingness to participate in this research study

These patients are all indicated with formal operative irrigation and debridement of their knee, regardless of study inclusion. However, they will be excluded from study inclusion if they meet one of the following exclusion criteria:

- Recently treated septic arthritis (within past 3 months)

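### Optional ROC cut-offs would be chosen for variables already screened at p<0.05 in the same patients (minimum 40), with no internal validation, so any reported accuracy will be optimistic on average

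*Combined protocol and SAP*

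**What the plan says.** The analysis text is item I (Methods of data analysis) of the study design section. It lists anticipated tests. For comparisons of means the criterion is "p values less than 0.05 will be considered to represent a significant difference", with no adjustment for the number of variables tested. Near the end it adds: "Receiver Operator Characteristic (ROC) may be calculated for significant continuous variables to determine the existence of a threshold that maximized sensitivity and specificity".

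The text does not name the binary outcome that the ROC curve would classify, the variables that are candidates, or the comparison in which a variable must be significant to qualify. It mentions no confidence interval, cross-validation, bootstrap or held-out set. The one reference to validation has institutional statisticians confirm the finalized data. That checks the analysis; it does not test a cut-off in new or resampled patients.

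The key variables (item F) include "initial presenting arthrocentesis labs as well as serum lab values", and also times, length of stay and Lysholm scores. One of the two laboratory routes into the trial is "AcrySTALLINE (without gout crystals) elevated synovial WBC >25,000 with high clinical suspicion"; the other requires more than 50,000 with 85% PMNs. On sample size, the power analysis "shows the optimal sample size to be a minimum of 40 patients".

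**The concern.** Two selections would be made on the same data. A variable is kept because its observed difference happened to be large enough for p<0.05, and its cut-off is then placed where the observed sensitivity and specificity are jointly best. Each step favours chance variation in the direction of good performance, and nothing planned removes the resulting optimism. With about 40 patients, and fewer still with whatever event is classified, that chance variation is large.

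At stake is a published cut-off that looks useful and performs much worse, or not at all, in the next series of patients. A simple threshold with sensitivity and specificity attached is easily reused.

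A second, separate issue is what such a cut-off would mean. Every participant has already met a synovial white cell limit and, on one route, a PMN limit. A threshold for either variable describes only patients who are already eligible.

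**Working it through.** **Inputs from the document.** Screen at p<0.05 per variable (item I; two-sided assumed, since sidedness is not stated). Minimum total of 40 (Indicate the number needed, and item B of the study design). Cut-off chosen to maximise sensitivity and specificity (item I).

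**Inputs assumed because the document gives none.** The outcome and its frequency (8, 10, 12 or 20 events in 40), the number of variables screened, and the true strength of each variable.

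**The plan's own figure.** The only figure is 40, described as "Power analysis utilized to determine a difference in the number of surgeries required to display apparent clinical resolution between open versus arthroscopic treatments". No effect size, SD or rate is given, so 40 cannot be reproduced. Back-solved for 20 per group, two-sided 0.05 and 80% power, it implies a standardized difference of (1.96 + 0.84) × √(2/20) = 0.886. No ROC accuracy is stated, so there is no planned value to compare with.

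**Step 1: chance of a false pass.** With k independent variables of no value, the chance that at least one reaches p<0.05 is 1 − 0.95^k: 23% for k = 5, 34% for 8, 40% for 10 and 54% for 15. If 8 variables are equally correlated at 0.3, 0.5 or 0.7, the 34% falls to about 30%, 25% or 19%.

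**Step 2: apparent against true accuracy.** Each simulated variable is normal with SD 1, shifted by d SD in patients with the event. It is kept only if a two-sample t-test gives p<0.05. The cut-off c maximises J = sensitivity + specificity − 1 in the same patients. For a variable that is higher in patients with events, the true J of that cut-off is Φ(c) − Φ(c − d). True AUC is Φ(d/√2), so AUC 0.65 corresponds to d = 0.545.

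| Patients / events | True strength | Share passing screen | Apparent J | True J at chosen cut-off |
|---|---|---|---|---|
| 40 / 8 | none (AUC 0.50) | 5% | 0.52 | 0 |
| 40 / 12 | none (AUC 0.50) | 5% | 0.46 | 0 |
| 40 / 10 | AUC 0.65 | 31% | 0.51 | 0.19 |
| 80 / 20 | AUC 0.65 | 55% | 0.39 | 0.20 |
| 40 / 12 | d = 0.8 | 62% | 0.52 | 0.28 |
| 40 / 12 | d = 1.2 | 92% | 0.58 | 0.42 |

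For the two rows with no true value, mean apparent AUC is 0.76 and 0.73. With 12 events, apparent sensitivity and specificity are about 75% and 71%. For the weak variable, J is overstated by 0.51 − 0.19 = 0.32 at 40 patients and by 0.39 − 0.20 = 0.19 at 80. At 40 patients its chosen cut-off has a 5–95% range about 1.5 SD wide. Over 8 to 20 events of 40 and d from 0 to 1.2, the overstatement of J runs from about 0.14 to 0.52.

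**Step 3: which step does it.** With 12 events and d = 0.8, choosing the cut-off without any screen overstates J by 0.445 − 0.272 = 0.17. Adding the screen raises this to 0.515 − 0.282 = 0.23. Both steps contribute.

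**Step 4: effect of the entry rule.** A variable with d = 0.8 was truncated from below in a large sample, 30% with the event. Its best achievable J falls from 0.31 to 0.22, 0.18 and 0.16 as the limit rises through 0, 0.5 and 1.0 SD above the mean of patients without the event. Restriction on entry lowers discrimination for the restricted variable; it does not raise it.

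**The case against.** The strongest reply is that this is an optional, secondary step. The ROC is permitted, not promised; it sits in a list of anticipated tests, and neither the hypothesis nor the specific aims mention a threshold. Harm requires the analysis to be run, a variable to pass, and the result to be published without caveat. All of that stands, and it limits the weight of the point. It does not remove the defect, because the condition that triggers the analysis is itself the selection on p<0.05.

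The sizes are also open to challenge. The no-value rows apply only to the roughly 1 in 20 such variables that pass. Forty is a minimum, and both a larger trial and a stronger variable shrink the optimism. The qualifying comparison is not stated, so testing each variable against a binary event is an assumption of the simulation. These objections are fair and are the reason for giving ranges. At 80 patients the weak variable's apparent J is still about twice its true value.

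Three stronger readings are tempting and are not supported:

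- A reader might infer that pre-selection on synovial white cell count causes the inflation. Step 4 shows that the effect on that variable runs the other way. Its effect on other variables depends on correlations that the document does not give.
- A reader might take the rule to be about laboratory biomarkers. It covers any significant continuous variable; presenting laboratory values are only the natural candidates.
- A reader might conclude that no synovial white cell or PMN threshold could ever be legitimate. A prognostic cut-off above the entry limit is valid within the enrolled population, and the second entry route sets no PMN limit.

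**Conclusion.** The point holds for the optional ROC analysis. If it is done as described, reported AUC, sensitivity and specificity will be optimistic on average, because the variable and its cut-off are selected in the same patients without internal validation. At 40 patients the apparent Youden index is about 0.46 to 0.52 for a variable of no value that passes the screen, and about 0.51 against 0.19 for one with true AUC 0.65; at 80 patients the latter is 0.39 against 0.20. These figures rest on assumed event counts, normally distributed variables and a two-sided t-test screen. The direction was the same in every scenario tried; the size cannot be fixed from the document.

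A reader might infer that the trial's main result is at risk. It is not: the ROC plays no part in comparing number of surgeries or length of stay between the open and arthroscopic groups. The entry restriction is a separate matter of interpretation: a synovial white cell or PMN threshold from this trial cannot be read as a diagnostic cut-off for unselected painful knees. This is a worthwhile, inexpensive improvement to a secondary analysis.

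**What to change.** Replace the ROC sentence in item I in one of two ways.

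1. Drop threshold-finding.
2. Keep it on these terms:
   - Name in advance one binary outcome (for example, any repeat surgery) and a short list of pre-operative variables, and analyse each whether or not it is significant.
   - Report AUC with a 95% interval, and bootstrap optimism-corrected AUC, sensitivity and specificity. Each bootstrap sample must repeat the choice of cut-off, and any screen that is retained.
   - Label the analysis exploratory.
   - State that any synovial white cell or PMN cut-off is prognostic within the enrolled population only.
   - If CRP or ESR is listed, use the presenting value, not follow-up values. Note that inflammatory blood markers that stay raised are themselves a criterion for failure of the first debridement (item E, Schedule of events), so an analysis of these markers against failure may be partly circular.

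The cost is one paragraph of text and a small amount of analysis work. The downside is that the reported accuracy will be lower. Treatment, recruitment and the main comparison are unchanged.
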